### 5.3.5. Analyses for Immunogenicity Data

Anti-PF-06671008 antibody data will be collected at baseline and post treatment according to the protocol.

## 5.4. Methods

### 5.4.1. Missing Data

In compliance with Pfizer standards, if the day of the month is missing for any date used in a calculation, the 1st of the month will be used to replace the missing date unless the calculation results in a negative time duration (eg, date of onset cannot be prior to day one date). In this case, the date resulting in 0 time duration will be used. Pfizer standards are also used if both month and day are missing (Jan 1 unless negative time duration). This excludes the pharmacokinetic, ECG, CCI which will only use the actual date collected or if date not available deem the data missing.

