6.3. Follow-up Visit

For follow-up procedures see [Schedule of Activities](#) and [Assessments](#) section. The EOT assessments are to be obtained if they are not completed in the last week (last 6 weeks for tumor assessments). The Follow-Up visit should be conducted at least 28 days, and no more than 35 days, after discontinuation of treatment. Patient will return to undergo assessments per the [Schedule of Activities](#) and will be evaluated for the resolution of any

treatment-related toxicity. Patients continuing to experience toxicity at this point following discontinuation of treatment will continue to be followed at least every 4 weeks until resolution or determination, in the clinical judgment of the investigator, that no further improvement is expected. Subsequent to the Follow-Up visit, patients should be contacted by telephone every 8 weeks (± 7 days) to obtain information on subsequent anti-cancer treatment and overall survival for up to two years after randomization.

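### SAP 5.4.1 sets no last-known-alive floor under a partial death date, so a death can be dated before a documented contact and OS is biased short

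*SAP*

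**What the plan says.** SAP 5.4.1 (Missing Data) applies "if the day of the month is missing for any date used in a calculation". The 1st "of the month will be used to replace the missing date unless the calculation results in a negative time duration". The illustration given is that "date of onset cannot be prior to day one date". When the guard fires, "In this case, the date resulting in 0 time duration will be used". If the month is missing as well, the replacement is "Jan 1 unless negative time duration". The readable exemptions are PK and ECG data and one redacted item, "which will only use the actual date collected or if date not available deem the data missing". Death dates are not named.

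Other places that bear on the point:

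- **SAP 5.4.2** handles missing time-to-event data by censoring and refers to Appendix 1. It lists the death date and the date of last contact.
- **SAP 6.3.1** analyses OS by Kaplan-Meier in the ITT set. Its only missing-data entry is censoring at the last visit.
- **SAP Appendix 1** covers PFS, duration of response, duration of stable disease and time to progression. It has no OS rules and does not mention partial dates. Death without progression is a PFS event only before treatment discontinuation or within 28 days of it (Table 3, footnote 2).
- **Protocol 6.3**: after the Follow-Up visit, "patients should be contacted by telephone every 8 weeks" for survival, for up to two years.

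**The concern.** The guard acts on the duration being calculated. For OS that runs from the start date to death, so the guard stops a death from being dated before the start. It does not stop a death from being dated before a visit or call at which the patient was recorded alive. The censoring rules do not help, because a patient known to have died on a partly known date is an event.

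The rule takes the first possible day, or the start date if that is later, so it can never date a death too late. The errors run one way, towards shorter OS. The dataset can also contain deaths that contradict contacts the sponsor already holds. Survival information gathered by telephone long after treatment is a plausible source of partial dates, although the documents give no rate.

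**Working it through.** The plan gives no figure on this point, so there is none to reproduce. The check applies the rule literally.

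**Formula.** Imputed death date = the later of (a) the 1st of the known month, or 1 January of the known year, and (b) the start date. OS = imputed death date − start date. The SAP does not define the OS start, so first dose is assumed.

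**Worked cases (dates are assumptions).** The last column uses the later of the first possible day and the day after last documented alive.

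| Start | Last documented alive | Death recorded as | Imputed by 5.4.1 | OS by rule (days) | Documented alive at day | OS with floor (days) |
|---|---|---|---|---|---|---|
| 10 Jan 2018 | 20 Sep 2018 | 2018 | 10 Jan 2018 (guard) | 0 | 253 | 254 |
| 20 Mar 2018 | 20 Sep 2018 | Sep 2018 | 1 Sep 2018 | 165 | 184 | 185 |
| 20 Mar 2018 | 1 Sep 2019 | 2019 | 1 Jan 2019 | 287 | 530 | 531 |
| 5 Mar 2018 | 19 Mar 2018 | Mar 2018 | 5 Mar 2018 (guard) | 0 | 14 | 15 |

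First row: 21 days left in January, then 28 + 31 + 30 + 31 + 30 + 31 + 31 for February to August, plus 20 in September = 253. Rows two and three show that OS stays above 0 when the known month or year is not that of the start. The death is then dated 184 − 165 = 19 and 530 − 287 = 243 days before the last contact.

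**PFS event status.** Suppose treatment stops on 20 August without progression, the patient is alive by telephone on 25 September, and death is recorded as September. The rule gives 1 September, 12 days after discontinuation and inside the 28-day window, so the death counts as a PFS event. The patient was in fact alive 36 days after discontinuation, so the death lies outside the window and PFS should be censored at the last tumor assessment before discontinuation.

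**Average size, among deaths with a partial date.**

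- Day missing, by hand: (30.4 − 1)/2 = 14.7 days.
- Month and day missing, by hand and ignoring the guard: (365 − 1)/2 = 182 days. This is too large, because for a death in the start year the loss cannot exceed the patient's own OS.
- With the guard, a simulation assumed exponential survival (median 6, 9 or 12 months), entry uniform over one calendar year, deaths within two years, and last contact on an 8-week or a weekly grid:

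| | Day missing | Month and day missing |
|---|---|---|
| Mean understatement of OS | about 14 days | 117 to 135 days |
| Dated before last known alive, 8-week contacts | 21–22% | 74–80% |
| Dated before last known alive, weekly contacts | 81–82% | 96–97% |
| OS = 0 | 4–6% | 37–49% |
| Mean understatement with a floor at last known alive, 8-week contacts | about 12 days | about 26 days |
| Same, weekly contacts | about 4 days | about 4 days |

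117/30.4 = 3.8 and 135/30.4 = 4.4, hence about 4 months.

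**Effect on one curve.** With 10 to 20 patients per indication, one false death at time 0 drops the Kaplan-Meier estimate by 1/20 = 5 to 1/10 = 10 percentage points from the origin.

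**The case against.** The best defence is that the error will be rare and will matter little.

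- **Frequency.** No document gives a rate of partial death dates. Calls are due every 8 weeks, and Protocol 6.4 asks for every effort to document outcome. In the first worked case the next call falls due around 15 November, which would normally narrow the month. This stands: year-only death dates are an edge case, and they supply the largest figures.
- **PFS.** Only deaths up to 28 days after discontinuation count, which largely overlaps the SAE reporting period with its 24-hour notification. Partial dates should be less common there. This stands, although the example shows that a later death can be pulled into the window.
- **Visibility.** Date of last contact and death date are both listed, so an impossible sequence could be noticed. That helps detection, but the analysis would still use the imputed date.
- **Consequence.** SAP 5.1 states no hypotheses, OS is a Part 2 secondary endpoint, and the Part 2 stopping guidance uses response counts. This stands.

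A reader might go further than the documents allow:

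- *That the only check is against Day 1.* The text bars any negative duration; Day 1 is its example. The gap is that time from last contact to death is not a duration the plan calculates.
- *That OS is generally set to 0, or cut by six months.* Zero requires the known month or year to match the start date's, and six months ignores the guard.
- *That adverse-event durations are distorted.* SAP 6.2.2 summarises events by number, percentage and worst grade; no duration summary is specified.
- *That new-therapy start dates should be forced past the last dose.* SAP 4.3 treats disallowed anticancer therapy during treatment as a major deviation, and such a rule could hide one.

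**Conclusion.** The point holds for partial death dates. Followed as written, SAP 5.4.1 can date a death before a documented contact, and no other section supplies a lower bound. OS is biased short, and a death's status as a PFS event can change.

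The averages of about 2 weeks and about 4 months apply only to deaths with partial dates and rest on the assumed survival and entry pattern. Complete death dates are unaffected. One exemption in 5.4.1 is redacted, so the conclusion rests on the readable text. The reach is the Kaplan-Meier estimates of OS and, to a lesser extent, PFS. The primary endpoints and the decision rules are not touched.

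**What to change.** Add to SAP 5.4.1: a partial death date is imputed as the later of the first day compatible with the recorded month or year and the day after the last date documented alive, capped at the last day that the recorded month or year allows. Flag imputed death dates in the listings.

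This removes deaths dated before a documented contact. It does not remove all of the shortening: with 8-weekly contact, the simulated day-only understatement falls only from about 14 to about 12 days.

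The cost is one sentence of SAP text, a line or two of programming and a listing flag. Date of last contact is already listed, so no new data are needed. No matching rule for adverse-event stop dates or new-therapy start dates is proposed.

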### 5.4.2. Efficacy Analysis

In this First In Patient study anti-tumor activity is a primary objective for Part 2 of the study.

Tumor response will be presented in the form of patient data listings that include, but are not limited to, tumor type, starting dose, tumor response at each visit, and best overall response. In addition, progression date, death date, date of first response and last tumor assessment date, and date of last contact will be listed.

The definition of each response category is provided in [Appendix 3](#) (RECIST v1.1) **CC1**

For the time-to-event endpoints, the missing data handling method will be censoring. Censoring rules for time-to-event endpoints are detailed in [Appendix 1](#).

#### **5.4.3. Pharmacokinetics**

##### **Concentrations below the limit of quantification**

In all data presentations (except listings), concentrations below the limit of quantification (BLQ) will be set to zero. (In listings BLQ values will be reported as “<LLQ”, where LLQ will be replaced with the value for the lower limit of quantification).

##### **Deviations, missing concentrations and anomalous values**

Patients who experience events that may affect their PK (eg, incomplete dosing) may be excluded from the PK analysis.

In summary tables and plots of median profiles, statistics will be calculated with concentrations set to missing if one of the following cases is true:

1. A concentration has been reported as ND (ie, not done) or NS (ie, no sample),
2. A deviation in sampling time is of sufficient concern or a concentration has been flagged anomalous by the pharmacokineticist.

Note that summary statistics will not be presented at a particular time point if more than 50% of the data are missing.

An anomalous concentration value is one that, after verification of bioanalytical validity, is grossly inconsistent with other concentration data from the same individual or from other subjects. For example, a BLQ concentration that is between quantifiable values from the same dose is considered as anomalous. Anomalous concentration values may be excluded from PK analysis at the discretion of the PK analyst.

##### **Pharmacokinetic parameters**

Actual PK sampling times will be used in the derivation of PK parameters. In the event that the actual sampling time is not available, the nominal time may be used if there is no evidence that the actual sampling time deviates substantially from the nominal time.

---

If a PK parameter cannot be derived from a subject's concentration data, the parameter will be coded as NC (ie, not calculated). (Note that NC values will not be generated beyond the day that a subject discontinues).

In summary tables, statistics will not be presented for a particular treatment group if more than 50% of the data are NC. For statistical analyses, PK parameters coded as NC will also be set to missing.

If an individual subject has a known biased estimate of a PK parameter (due for example to an unexpected event such as vomiting before all the drug is absorbed in the body), this will be footnoted in summary tables and will not be included in the calculation of summary statistics or statistical analyses.

## **6. ANALYSES AND SUMMARIES**

### **6.1. Standard Analyses**

#### **Study Conduct and Patient Disposition**

An accounting of the study patients will be tabulated. The subject evaluation groups will be listed. The Full Analysis Set will be used.

Subject discontinuation from treatment and study will be tabulated and listed separately with their reason for discontinuation. The Safety Analysis Set will be used.

#### **Baseline Characteristics**

Baseline characteristics such as demographics, prior medication, medical history, ECOG performance status, and primary diagnosis will be tabulated and listed. For ECOG performance status a shift table (worst post-baseline vs baseline may be produced). The Safety Analysis Set will be used.

#### **Treatment Administration/Compliance**

Listings and tables by dose level will be provided. The safety analysis set will be used.

Dose modifications may occur in the following ways:

- Cycle delay;
- Dose delay within a Cycle;
- Dose reduction—A decrease in the administered total daily dose (non-zero) compared to the planned total daily dose upon enrollment. If in the CRF the prescribed dose unit is mg/kg, but the actual dose is in ng the actual dose ng/kg should be calculated considering the body weight of the patient at that visit.

The following will be summarized by patient for overall and each dose level:

- Number of subjects per dose level (Prime and non-Prime);
- Median and range of number of cycles started per subject;
- Number (%) of subjects starting a cycle (1, 2, 3...);
- Number (%) of patients with cycle delays;
- Number (%) of dose interruptions (include both known and unknown dates);
- Number (%) of patients with dose reductions;
- Number (%) of each reason (drug related AE vs AE vs. Other) for cycle delays, dose interruptions and dose reductions;
- Time on treatment (median, range).

The following will be summarized by cycle:

- For ongoing subjects, the last cycle end date is the cycle start date + number of days per cycle - 1 day;
- For completers and discontinued subjects, if the Systemic Therapy dataset exists , the end date would be the earliest date of the start date of the new anticancer treatment or last active treatment + 27 days. If the Systemic Therapy SCRF data does not exist then the last cycle end date will be set to last active treatment + 20 days;
- Total number of cycles started;
- Total number of doses;
- Number of cycles and doses started per patient (median, range);
- Number of cycles and doses before 1st delay (median, range);
- Number of cycles and doses before 1st reduction (median, range);
- Number of cycles and doses before 1st interruption (median, range).

The following will be summarized for cumulative dose by dose level and cycle:

- Summary statistics (mean, median, standard deviation and range) of cumulative dose and percent of starting dose (compared to Day 1 dose of each cycle).

Listings by patient (ordered by dose level): start date and stop date of each dosing period within each cycle (including records with 0 ng), administered total daily dose for each period, any missed doses, number of missed doses, reason for any dosing changes.

Listings by patient and each cycle (ordered by dose level): cycle length, total planned dose, administered total dose, percentage of planned dose, dose delay (yes/no), dose reduction (yes/no), dose interruption (yes/no), and infusion rate and reason for infusion rate changes.

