This is a Phase 1, open-label, multi-center, multiple-dose, safety, PK CCI study of single-agent PF-06671008. This study contains two parts, dose escalation (Part 1) followed by dose expansion (Part 2). Sequential cohorts of patients with tumor types with the potential to have P-cadherin expression (see [Appendix 2](#)), and that are not candidates for regimens known to provide clinical benefit, will receive escalating doses of PF-06671008, in Part 1 of the study. In addition, at clinically relevant dose levels with the IV or SC route of administration of 100 ng/kg or higher (ie, doses where the exposure is near the target effective exposure) where the safety is confirmed in the first 2-4 patients dosed, approximately up to 5 additional patients with colorectal, triple negative breast, non-small cell lung cancer or squamous cell carcinoma of the head and neck may be enrolled. Pfizer internal data shows high level of P-cadherin is frequently found in these tumors. Paired biopsies will be required for these additional patients. Part 2 will evaluate the dose selected from Part 1 in patients with P-cadherin expressing TNBC, CRC or NSCLC.

Up to approximately 152 patients are expected to be enrolled in the study overall. The actual number of patients enrolled will depend on the tolerability of PF-06671008 and the number of dose levels required to identify the MTD.

PF-06671008 will be administered as a weekly intravenous (IV) infusion in 21-day cycles with a starting dose of 1.5 ng/kg. There will be a minimum 72-hour interval between the first dose administered to each of the initial patients (ie, patients contributing to initial DLT evaluation) enrolled at a new dose level due to the unknown time course of possible infusion-related reaction or cytokine release. All patients will be observed in-patient for at least 24 hours after the first dose on Cycle 1 Day 1 (C1D1). At doses of 100 ng/kg or higher, especially when the total dose exceeds 10,000 ng, additional in-patient overnight observation for subsequent doses beyond C1D1 may be considered based on the investigator's discretion and should be discussed with Pfizer.

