5.4.5. Recommended Dose Modifications

Every effort should be made to administer investigational product on the planned dose and schedule.

In the event of significant toxicity dosing may be delayed and/or reduced as described below. In the event of multiple toxicities, dose modification should be based on the worst toxicity observed. Patients are to be instructed to notify investigators at the first occurrence of any adverse symptom.

Dose modifications may occur in one of three ways:

- Within a cycle: dosing interruption until adequate recovery and dose reduction, if required, during a given treatment cycle;
- Between cycles: next cycle administration may be delayed due to persisting toxicity when a new cycle is due to start;
- In the next cycle: dose reduction may be required in a subsequent cycle based on toxicity experienced in the previous cycle.

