*In addition, observation of a confirmed CRS event that meets the above qualifications following later infusions (ie, after Cycle 1 Day 1) or CRS events that are approaching the limit of tolerability may prompt the investigators and sponsor to include evaluation of a Dose Prime for subsequent cohorts.*

*After confirmation of the safety of Dose Prime, the treatment schedule will implement the inclusion of the fixed priming dose as the first dose (C1D1) followed by a second dose (C1D8) that will continue to be escalated in subsequent cohorts following an mTPI method in cohorts of 2-4 patients. After the MTD has been established, the priming dose may potentially be further verified in connection to the established MTD/RP2D, including consideration of more than one priming step, if indicated, using information from all patients who were included in the initial priming dose determination as well as those enrolled in subsequent dosing cohorts.*

*The primary DLT observation period for cohorts that include Dose Prime will be 21 days following the first dose (C1D1). The dose escalation should a Dose Prime be instituted is depicted in Figure 2.*

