**Figure 2 Study Schematic Should Dose Prime Be Explored**

DL = Dose Level

\* In-patient observation applies to all cohorts

\*\* Dose level 1 will be higher than Dose Prime

\*\*\* Dose level 2 will be higher than Dose Level 1

*For cohorts instituting a Dose Prime, there will be a 72 hour observation period between the first dose administered to each of the initial patients enrolled (ie, patients contributing to initial DLT evaluation) at a new dose level. In addition to in-patient observation following the C1D1 dose, patients enrolled in cohorts instituting a Dose Prime must also undergo in-patient observation for at least 24 hours (for cohorts where PF-06671008 will be administered IV) or 48 hours (for cohorts where PF-06671008 will be administered SC) following the C1D8 dose.*

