### 2.3.1. Recommended Phase 2 Dose (RP2D) Definition

*The RP2D is the dose chosen for further study based on Phase 1 study results. If the MTD proves to be clinically feasible for long-term administration in a reasonable number of patients, then this dose usually becomes the RP2D. Further experience with the MTD may result in a RP2D dose lower than the MTD (eg, if in the expansion part >25% of patients require a dose reduction due to toxicity, then the sponsor and investigator determine if a lower RP2D needs to be determined).*

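### SAP 6.1 summarises dose against each cycle's own Day 1 dose, so a fully dosed primed Cycle 1 reads above 100% and a dose reduced at the start of a cycle reads as 100%

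*SAP*

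**What the plan says.** SAP 6.1, Treatment Administration/Compliance, introduces one block of exposure statistics with "The following will be summarized for cumulative dose by dose level and cycle". Within it, mean, median, standard deviation and range are given for cumulative dose and for "percent of starting dose (compared to Day 1 dose of each cycle". No other percentage of dose receives summary statistics. The same section separates primed from non-primed patients when it counts subjects, but it gives the percentage no separate rule for primed cohorts or for patients whose dose has been reduced.

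Two other outputs in that section use a different reference. A dose reduction is a non-zero administered dose that is lower "compared to the planned total daily dose upon enrollment", and patients with reductions are counted on that basis, with reasons. A listing by patient and cycle shows planned dose, administered dose and the ratio of the two as a percentage.

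On priming, SAP 2.2.2 describes the "inclusion of the fixed priming dose as the first dose (C1D1) followed by a second dose (C1D8) that will continue to be escalated", and the notes to SAP Figure 2 say "Dose level 1 will be higher than Dose Prime". On reductions, Protocol 5.4.5 says that a "dose reduction may be required in a subsequent cycle based on toxicity experienced in the previous cycle". Protocol 5.4.8 adds that a reduced dose carries into all later cycles and may not be raised again.

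**The concern.** A percentage of this kind should show how much of the intended dose was delivered. The reference chosen here fails at that in two situations that the trial expects.

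- **Primed Cycle 1.** Day 1 is deliberately a lower dose than Days 8 and 15. Using it as the reference pushes the percentage above 100% for a patient treated exactly to plan, and can hide a dose that was not given.
- **A dose reduced at the start of a cycle.** Day 1 of that cycle, and of every later cycle, is already the reduced dose. The numerator and denominator fall together, and the reduction disappears from the percentage.

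At stake is whether a reader of the exposure table gets a correct picture of delivered dose. Mixing primed and non-primed patients within a dose level would also make the Cycle 1 mean and standard deviation hard to interpret.

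**Working it through.** The documents give no figure for this quantity, so there is none to reproduce. The check applies the stated rule and compares it with dose delivered as a share of plan.

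**Inputs**
- Three doses per cycle (Days 1, 8 and 15), from "PF-06671008 will be administered as a weekly intravenous (IV) infusion in 21-day cycles with a starting dose of 1.5 ng/kg" in the Protocol Summary, Study Design.
- Priming dose P on Cycle 1 Day 1, then assigned dose T, with T > P (SAP 2.2.2 and Figure 2).
- Dose grid 1.5, 7.5, 20, 50, 100, 200, 300, 400 ng/kg (SAP Table 1). No priming dose is fixed in the documents, so the pairs below are illustrations.
- Scaling, assumed: the denominator is 3 × the Day 1 dose of the cycle. The SAP does not say this. Without it, an ordinary full cycle at a constant dose reads 3T/T = 300%.

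**Primed Cycle 1**

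All doses given: (P + 2T)/(3P), which exceeds 100% whenever T > P.

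| P, then T (ng/kg) | Given | Against 3 × Day 1 | Against plan (P + 2T) |
|---|---|---|---|
| 300, 400 | all three | 1100/900 = 122% | 1100/1100 = 100% |
| 100, 200 | all three | 500/300 = 167% | 500/500 = 100% |
| 100, 400 | all three | 900/300 = 300% | 900/900 = 100% |
| 100, 200 | Day 15 missed | 300/300 = 100% | 300/500 = 60% |

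The smallest ratio T/P on the grid is 400/300, so 122% is the lowest value for a fully dosed primed Cycle 1 on that grid.

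The excess has limits. With Day 15 missed, (P + T)/(3P) exceeds 100% only if T > 2P. With Days 8 and 15 both missed, the figure is P/(3P) = 33%. From Cycle 2 onwards Day 1 is no longer the priming dose, and full dosing gives 3T/(3T) = 100%.

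**Reduction at the start of a cycle, all three doses given at the lower level R instead of T**

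Rule as written: 3R/(3R) = 100% in every case. Against the enrolled dose: 3R/(3T) = R/T.

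| T to R, one level (ng/kg) | As written | Against enrolled dose |
|---|---|---|
| 400 to 300 | 100% | 75% |
| 300 to 200 | 100% | 66.7% |
| 200 to 100 | 100% | 50% |
| 100 to 50 | 100% | 50% |
| 50 to 20 | 100% | 40% |
| 20 to 7.5 | 100% | 37.5% |
| 7.5 to 1.5 | 100% | 20% |

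**Reduction within a cycle.** A cut from 300 to 200 ng/kg at Day 8 reads (300 + 200 + 200)/900 = 77.8% in that cycle. The next cycle reads 100%, when the patient is receiving 66.7% of the enrolled dose.

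**The case against.** The strongest reply is that little depends on this percentage. Reductions are counted separately against the dose planned at enrolment, absolute cumulative dose is summarised by dose level and cycle, and the planned-dose percentage is already listed by patient and cycle. SAP 5.1 has no hypotheses, and the exposure table is descriptive. Priming is optional, and the wording is terse enough to allow other readings. All of this stands, and it limits the size of the point. It does not rescue the statistic: the one percentage that is summarised still answers the wrong question. If the phrase instead meant each cycle's Day 1 dose as a percentage of the Cycle 1 Day 1 dose, a reduction in an unprimed patient would show, but primed patients would then read above 100% in later cycles too.

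Three stronger conclusions might be inferred, and the documents do not support them.

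- **That the RP2D example is undermined.** SAP 2.3.1 speaks of a lower dose "if in the expansion part >25% of patients require a dose reduction due to toxicity". That is a count of patients and does not use this percentage. A patient cut from 400 to 300 ng/kg at Cycle 2 Day 1 is counted as reduced whatever the percentage shows.
- **That reductions in primed patients will be missed**, because the dose planned at enrolment could be taken as the Cycle 1 Day 1 dose. Nothing in the SAP equates the two. Protocol 5.1 has the sponsor assign a dose level, SAP Figure 2 keeps Dose Prime apart from the dose levels, and Protocol 5.4.8 expresses reductions in dose levels. What remains is that a primed patient has two planned doses while the definition refers to one, which calls for a clarifying sentence.
- **That primed patients exceed 100% throughout.** The excess is confined to Cycle 1.

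**Conclusion.** The point holds as a small defect in a descriptive summary. Followed as written, the rule puts a fully dosed primed Cycle 1 above 100% (at least 122% on the Table 1 grid), can mask a missed dose (100% shown against 60% of plan), and reports 100% for a fully dosed patient reduced at the start of a cycle, when delivery is 20% to 75% of the enrolled dose for one level down.

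The Cycle 1 percentages rest on the factor of three and on illustrative dose pairs. The direction of the Cycle 1 effect needs only T > P. The reduction result needs only that all doses of the cycle are given at the lower level. The DLT, MTD and response analyses are unaffected.

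**What to change.** In SAP 6.1, replace the summarised percentage with administered dose as a percentage of the dose planned at enrolment for that cycle, which is the quantity the section already lists by patient and cycle. Define planned dose by visit: in primed cohorts, the priming dose on Cycle 1 Day 1 and the assigned dose afterwards; in other cohorts, the assigned dose throughout. State that this planned dose does not change when a patient's dose is reduced. Use the same visit-specific dose as the reference when counting reductions in primed patients.

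The cost is one line and one definition in the SAP, plus minor programming. No new data are needed and no treatment rule changes.
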